**Table 12 Mandatory CRS Prophylaxis** 

			Glucocorticosteroids	Antihistamines	Antipyretics
	1st GEN1044 administration	Day 01*	Prednisolone 100 mg IV†	Diphenhydramine 50 mg IV or PO (or equivalent)	Paracetamol (acetaminophen) 650 to 1000 mg PO (or equivalent)
Cycle 1	2 nd GEN1044 administration	Day 08*	Prednisolone 100 mg IV†	Diphenhydramine 50 mg IV or PO (or equivalent)	Paracetamol (acetaminophen) 650 to 1000 mg PO (or equivalent)
	3 rd GEN1044 administration	Day 15*	Prednisolone 100 mg IV†	Diphenhydramine 50 mg IV or PO (or equivalent)	Paracetamol (acetaminophen) 650 to 1000 mg PO (or equivalent)
Cycle 2	4 th GEN1044 administration	Day 01*	Yes, if CRS ≥ grade 2 occurred following the 3 rd GEN1044 administration at C1D15, administration of glucocorticosteroids is continued in Cycle 2 until no subsequent CRS develops.	Yes, if glucocorticosteroids are administered	Yes, if glucocorticosteroids are administered

\* 30 minutes to 2 hours prior to administration of GEN1044.

# **6.3** Dosages and Administration

Trial treatment should be administered as described in Section 4.2 (Dose Escalation) and Section 4.3 (Expansion) until one or more of the discontinuation criteria in Section 8.1 are met:

- Cycles 1 through 4: Days 1, 8, and 15 (once weekly for a 21-day cycle)
- Cycles 5 and beyond: Day 1 (every 3 weeks for a 21-day cycle)

Refer to the preparation and administration guideline for additional information and stepwise guidance on dosage and administration.

Detailed dose modification guidance is provided in Section 7. Refer to Section 6.5 for information regarding concomitant therapy.

GEN1044 will be administered using IV infusion on Days 1, 8, and 15 of each 3-week (21-day) treatment cycle. GEN1044 will be administered as a fixed dose. In the Dose Escalation part, subjects will be administered GEN1044 according to dose levels outlined in Section 4.2. In the Expansion part, subjects will be administered GEN1044 with the recommended dose from the escalation.

As a routine precaution, subjects dosed with GEN1044 must be monitored during infusion and treated in an area with resuscitation equipment and emergency agents. For weekly dosing during Cycle 1 and Cycle 2, all subjects must be observed for at least 4 hours after ending infusion of GEN1044. For all subsequent cycles, subjects must be observed for at least 2 hours after ending infusion of GEN1044. See Section 4.2 for additional details regarding when an overnight stay (24 hours in-hospital observation) is required.

Refer to the administration and preparation guideline in the GCT1044-01 IMP Manual for additional guidance on trial drug preparation, handling, and storage.

† or equivalent, including oral dose.

Version: 4.0

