### 4 TRIAL DESIGN

# 4.1 Description of Trial Design

This is a first-in-human (FIH), open-label, multinational, multicenter phase 1/2a trial to evaluate the safety, PK, pharmacodynamics, and preliminary efficacy of GEN1044. GEN1044 will be administered as an IV infusion to a mixed population of subjects with solid tumors. The trial consists of 2 consecutive parts: a Dose Escalation (phase 1) and an Expansion (phase 2a).

In the Dose Escalation part, subjects will be administered GEN1044 according to dose levels outlined in Section 4.2. In the Expansion part, subjects will be administered GEN1044 with the recommended dose(s) from the escalation. GEN1044 will be administered via IV infusion weekly (Q1W) for the first 4 cycles (each cycle is 21 days), followed by every 3 weeks (Q3W), thereafter. Cycle 1 will consist of a priming dose, an intermediate dose, and a full dose. Alternatively, when necessary, Cycle 1 will consist of a priming and 2 intermediate doses, with the first full dose administered on Cycle 2 Day 1. The decision as to whether 1 intermediate dose or 2 intermediate doses will be used for a given cohort will be based on the recommendation of the DEC and confirmed by the Safety Committee (see Section 10.10).

In both parts, subjects will continue to receive GEN1044 until any of the protocol-defined treatment discontinuation criteria are met (refer to Section 8.1). Different doses and schedules might be explored during the Dose Escalation and/or Expansion parts based on the data generated in the dose escalation. Efficacy will be assessed by on-treatment radiological exams/imaging every 6 weeks (±7 days) for 36 weeks, and every 12 weeks (±7 days) thereafter until PD as assessed by the investigator, the start of new anti-cancer therapy, withdrawal of consent, or death, whichever occurs first. For subjects with prostate cancer, efficacy will also be assessed by on-treatment bone scans every 6 weeks (+7 days) (or longer per local standards) for 24 weeks, and every 12 weeks (±7 days) thereafter until PD, the start of new anti-cancer therapy, withdrawal of consent, or death, whichever occurs first. Response assessment criteria relevant to the tumor type (eg, RECIST v1.1 criteria) (Eisenhauer et al., 2009) will be used for response evaluation. Images may be submitted to a central imaging vendor if additional analyses are conducted.

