#### 11.4 Treatments

The FAS will be used for the analyses below. Categorical data will be summarized as frequencies and percentages. For continuous data, mean, standard deviation, median, 25th and 75th percentiles, minimum, and maximum will be presented.

Version: 4.0

The duration of exposure to GEN1044, the cumulative dose administered, and dose intensity (computed as the ratio of actual cumulative dose received and number of cycles initiated) will be summarized by means of descriptive statistics.

The number of subjects with dose adjustments and the reasons will be summarized, and all dosing data will be listed.

Concomitant medications and significant non-drug therapies prior to and after the start of the trial treatment will be listed and summarized according to the anatomical therapeutic chemical (ATC) classification system.

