3.3 Treatment administration schedule

GEN1044 will be infused intravenously in 21-day cycles, as per Section 4.1 of the protocol:

- Cycle 1-4: Day 1, 8, and 15
- Cycles 5 and later: Day 1 only

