5.3 Calculation of durations

Durations in months will be calculated as durations in days by dividing by 30.4375.

Time from initial diagnosis will be calculated in years, from the date of initial diagnosis to the date of the first dose date: (first dose date – date of initial diagnosis) /365

Total treatment duration will be calculated in days as:

- If last cycle is Cycle 1, 2, 3 or 4: last dose date first dose date + 7
- If last cycle is Cycle 5 or later: last dose date first dose date + 21

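### Protocol Section 6.3 gives two dosing frequencies from Cycle 5 onward (one or three infusions per 21-day cycle), and the two statements must be reconciled

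*Protocol*

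**What the plan says.** Section 6.3 of the current protocol (version 4.0) opens with two bullets. The first reads "Cycles 1 through 4: Days 1, 8, and 15 (once weekly for a 21-day cycle" and the second "Cycles 5 and beyond: Day 1 (every 3 weeks for a 21-day cycle". Two short paragraphs later the section states "GEN1044 will be administered using IV infusion on Days 1, 8, and 15 of each 3-week (21-day) treatment cycle", without restricting it to the first four cycles.

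Other places that state the schedule:

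- Protocol synopsis and Section 4.1: weekly "for the first 4 cycles (each cycle is 21 days), followed by every 3 weeks (Q3W), thereafter".
- Protocol Tables 1 and 5: under Cycle 5 to progression, the GEN1044 administration row is marked on Day 1 only.
- SAP Section 3.3: "Cycles 5 and later: Day 1 only".

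Two further provisions depend on the interval between doses. Protocol Table 2 (Dose Escalation) takes PK samples on C5D8 and C5D15, defined as 168 and 336 hours after the end of the C5D1 infusion. SAP Section 5.3 computes treatment duration as last dose date minus first dose date, plus 7 days if the last cycle is 1 to 4 and plus 21 days if it is Cycle 5 or later.

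**The concern.** Section 6.3 is the protocol's operative dosing section, and from Cycle 5 its two statements cannot both be followed. The section refers the reader to Sections 4.2 and 4.3 for how treatment is given, but in the text available neither mentions the change of frequency at Cycle 5, so those references do not settle it. The trial is first-in-human, and the sentence is an instruction rather than background.

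Three things would be at stake if a site acted on the later sentence:

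- Subjects reaching Cycle 5 would receive infusions that the visit schedule does not show.
- In Dose Escalation, the two late Cycle 5 PK samples could follow an infusion other than the one they are timed from. They help describe the terminal part of the profile after C5D1, and half-life and AUC are secondary endpoint parameters. Table 1 already has escalation subjects attending on C5D8 and C5D15, so the absence of a visit would not prevent an extra infusion.
- The 21-day tail in the SAP duration rule assumes a three-week interval that would not apply to those subjects.

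**Working it through.** The plan gives no figure to reproduce. The check is a count of infusions under each statement, followed by its effect on the provisions that depend on it.

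**Inputs.** Bullets in Section 6.3: 3 infusions per cycle in Cycles 1 to 4, then 1 per cycle. Later sentence in Section 6.3: 3 infusions in every cycle. Cycle length: 21 days.

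**Formulas for cumulative infusions through cycle c.**
- Bullets: A(c) = 3 × min(c, 4) + max(c − 4, 0)
- Later sentence: B(c) = 3 × c

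| Through cycle | Bullets A(c) | Later sentence B(c) | B/A |
|---|---|---|---|
| 4 | 12 | 12 | 1.00 |
| 5 | 12 + 1 = 13 | 15 | 1.15 |
| 8 | 12 + 4 = 16 | 24 | 1.50 |
| 12 | 12 + 8 = 20 | 36 | 1.80 |
| 17 | 12 + 13 = 25 | 51 | 2.04 |

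From Cycle 5 the ratio within a cycle is 3/1 = 3. The cumulative ratio stays below 3 because the first 12 infusions are common to both.

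**DLT evaluation.** The DLT period is 21 days, or 28 days with two intermediate doses (Section 7.1). It ends in Cycle 1 or early in Cycle 2, where the two statements agree. There is no effect.

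**PK samples (Table 2, escalation only).** With an infusion on C5D8, the 336-hour sample on C5D15 would come after that second infusion. The 168-hour sample falls on the day of the infusion itself. Its window is +72 hours, so it could be drawn before or after, depending on the clock time.

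**Duration rule (SAP Section 5.3).** If dosing were weekly in Cycle 5 or later, the tail consistent with the SAP's own weekly convention would be 7 days, and the rule adds 21. The difference is 21 − 7 = 14 days per affected subject. Both dose dates in the formula are actual dates, so only the tail is involved.

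**Exposure summaries.** Protocol Section 11.4 defines dose intensity as "computed as the ratio of actual cumulative dose received and number of cycles initiated", and SAP Section 8.2 summarises the number of doses and the cumulative dose administered. Both use doses given. Extra infusions would raise these values, and the raised values would be a correct record of what happened.

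**The case against.** The strongest reply is that one loosely worded sentence stands against explicit cycle-by-cycle text everywhere else. The bullets come first in the same section and treat Cycles 1 to 4 and Cycle 5 onward separately. The synopsis, Section 4.1, the administration rows of Tables 1 and 5 and SAP Section 3.3 all agree with them. In Expansion, Table 5 marks nothing on Days 8 and 15 from Cycle 5. In Dose Escalation, Table 1 limits later Day 8 and Day 15 activities to Cycle 5, and the Table 2 PK times presuppose no intervening dose. A site would have to pass over all of this to act on the sentence, which may be residual wording. Section 6.3 also points to a separate preparation and administration guideline that is not available here. Enrolment was stopped after the safety review of 29 September 2021 (SAP Section 1.2), and no expansion data were collected (SAP Section 2.2).

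Most of this stands. It makes a misreading less likely and confines the reach to escalation subjects who got to Cycle 5. It does not remove the contradiction, because the sentence remains an unqualified instruction in the section on dosing.

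A reader might go further and infer that exposure, safety results and treatment duration would be wrong. The documents do not support that. Exposure is tabulated from doses given, safety events are recorded as they occur, only the duration tail could be off, and no SAP analysis adopts the later sentence. Nor do the documents show that any subject was dosed on Day 8 or Day 15 from Cycle 5.

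**Conclusion.** The contradiction is real, lies in current protocol text and should be corrected. From Cycle 5 it amounts to 3 against 1 infusions per 21-day cycle, or 13 against 15 cumulatively through Cycle 5 and 16 against 24 through Cycle 8. A reader might take the factor of three as a difference in total dose, but it applies only within cycles from Cycle 5.

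The consequences depend on a site having followed the later sentence. In that case the C5D8 and C5D15 PK samples could be confounded, and the duration variable could be too long by up to 14 days per affected subject. Cycles 1 to 4 and the DLT endpoint are untouched. The number of subjects who reached Cycle 5 is not given, so the practical reach cannot be sized.

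This is an internal-consistency error in the protocol. It is not a weakness of design, since every other statement of the schedule listed above agrees. The conclusion takes no position on which frequency is clinically right.

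**What to change.** Reconcile the later sentence in Protocol Section 6.3 with that section's bullets, the synopsis, Section 4.1, Tables 1 and 5 and SAP Section 3.3, so that a single schedule is stated throughout. The sponsor must decide and confirm which schedule was intended.

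Check the dosing records of every subject who reached Cycle 5 for infusions on Day 8 or Day 15. If any are found, report them, flag the affected C5D8 and C5D15 PK samples, and state how the SAP Section 5.3 tail is applied to those subjects.

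The cost is one protocol sentence and a record check limited to escalation subjects with at least five cycles. No sample size or DLT rule changes.

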#### 6.4 Compliance

GEN1044 will be administered by site personnel to assure compliance with trial requirements.

# 6.5 Concomitant Medications and Therapies

The subject must be told to notify the trial site about any new medications (including over-the-counter or prescription medicines, vitamins, and vaccines) they take after the start of GEN1044. All medications (other than GEN1044) and significant non-drug therapies (including physical therapy, herbal/natural medications and blood transfusions) administered during the trial (ie, beginning with administration of the first dose of trial drug until 30 days after the last dose of trial drug) must be documented.

Investigators may prescribe concomitant medications or treatments deemed necessary to provide adequate supportive care except for those medications identified as "prohibited" (Section 6.5.3).

# 6.5.1 Permitted Concomitant Medications and Therapies

The following concomitant medication and therapies are permitted during the trial:

- Local palliative radiotherapy on non-target lesions.
- G-CSF and other hematopoietic growth factors may be used in the management of acute toxicity, such as febrile neutropenia and ≥ grade 3 neutropenia, when clinically indicated or at the investigator's discretion. In case of recurring ≥ grade 3 neutropenia, use of growth factors is mandated.
- Blood cell transfusion, if clinically indicated.
- Multivitamins, vitamin D, calcium and supplements in prevention of weight loss.
- Prescribed medicinal cannabinoids as palliative therapy

# 6.5.2 Permitted Concomitant Therapy Requiring Caution and/or Action

Concomitant medications are allowed to provide adequate care and may be given as clinically indicated. All concomitant medication should be recorded. Name, indication (reason for use) and dates of administration (start and end dates) of concomitant therapies will be documented. If parenteral nutrition is given during the trial, the individual components do not need to be specified in detail, indication as "parenteral nutrition" is sufficient. If a subject needs general anesthesia, it will be sufficient to indicate "general anesthesia" without specifying the details.

The Medical Officer should be contacted if there are any questions regarding concomitant medication or prior therapy.

The trial site will ensure supportive medication, eg, premedication, anti-viral medication, anti-IL-6R.

# 6.5.2.1 Supportive Care for Cytokine Release Syndrome

Rescue medication in terms of an antidote to reverse the action of GEN1044 is not available.

Potential side effects of GEN1044 have to be treated symptomatically.

For treatment of CRS subjects should receive supportive care according to Appendix 6 (Table 26) and local guidelines. The supportive care can include, but is not limited to:

Version: 4.0

- Infusion of saline
- Systemic glucocorticosteroid, antihistamine, antipyretic(s)
- Support for blood pressure (vasopressin, vasopressors)
- Support for low-flow and high-flow oxygen and positive pressure ventilation
- Monoclonal antibody against IL-6R, eg, IV administration of tocilizumab
- At investigator's discretion: Monoclonal antibody against IL-6 (siltuximab) or IL-1R (anakinra), if not responding to repeated tocilizumab (3 doses within 24 hours).

Blood product support, analgesics, skin and mouth care, etc, should be according to local guidelines and the investigator's discretion.

CRS should be graded according to Table 16 (see Section 10.4.1).

#### 6.5.2.2 Growth Factors

The use of growth factors for neutropenia such as G-CSF will be allowed during treatment with GEN1044. In case of recurring grade 3 neutropenia, use of growth factors is mandated.

# 6.5.3 Prohibited Concomitant Therapy

The following medications are prohibited during the trial (from first dose):

- Any other anti-cancer therapy, eg, chemotherapy, immunotherapy, radiotherapy or experimental therapy. Local palliative radiotherapy on non-target lesions is allowed.
- Corticosteroid that exceed a total daily dose of 10 mg of prednisolone or equivalent administered for more than 10 days unless for the management of AEs (excluding corticosteroids given as premedication or CRS therapy).
- Herbal preparations or related over-the-counter (OTC) preparations containing herbal ingredients are not permitted during participation in the trial.
- Anti-CD3 antibodies.
- Live attenuated vaccines while participating in the trial and for 3 months following the last dose of GEN1044. Note: Seasonal influenza vaccines are generally killed virus vaccines and are permitted however, intranasal influenza vaccines are live attenuated and are not allowed.
- SARS-CoV-2 vaccine administration during the DLT assessment period.

The sponsor must be notified in advance (or as soon as possible thereafter) of any instances in which prohibited therapies are administered. If a subject receives any of these during the trial, the sponsor must be notified for evaluation of whether the subject can continue treatment in the trial.

#### 6.6 **GEN1044 Information**

#### 6.6.1 Physical Description of GEN1044

The GEN1044 supplied for this trial is a liquid formulation provided at 10 mg/mL. It will be manufactured and provided under the responsibility of the sponsor.

#### 6.6.2 Packaging

GEN1044 - 10 mg/mL is formulated as a concentrate for solution for infusion to be diluted (at the site) in GEN buffer diluent

Version: 4.0

The drug product will be provided to the site/pharmacy in a glass vial containing 5 mL of GEN1044 (50 mg/vial).

## 6.6.3 Labeling

GEN1044 labels will contain information to meet the applicable regulatory requirements. For further details see the trial-specific preparation and administration guideline in the GCT1044-01 IMP Manual.

# 6.6.4 Preparation, Handling, and Storage

The preparation, handling and storage of GEN1044 are described in the GCT1044-01 IMP Manual. GEN1044 must be stored at controlled temperatures ranging from 2°C to 8°C (35.6°F to 46.4°F).

## 6.6.5 Drug Accountability

The investigator or designee must maintain an accurate record of the shipment and dispensing of trial treatment in a drug accountability log. Drug accountability will be verified by the field monitor during site visits and at the completion of the trial.

When drug accountability has been verified and a copy of the completed drug accountability log has been received by sponsor, the investigator will dispose all used and unused trial treatment and packaging in accordance with the guidance in the GCT1044-01 IMP Manual and local regulations.

# 6.6.6 Handling of Other Trial Treatment

Not applicable.

# 6.7 Technical Complaint Handling

A technical complaint is defined as any suspicion of a product defect related to manufacturing, labeling, or packaging, ie, any dissatisfaction relative to the identity, quality, durability, or reliability of a product, including its labeling or package integrity. A technical complaint may have an impact on the safety and efficacy of the product. Timely, accurate, and complete reporting and analysis of technical complaint information from trials are crucial for the protection of subjects, investigators, and the sponsor, and are mandated by regulatory agencies worldwide. The sponsor has established procedures in conformity with regulatory requirements worldwide to ensure appropriate reporting of technical complaint information; all trials conducted by the sponsor or its affiliates will be conducted in accordance with those procedures.

#### 6.7.1 Procedures

All initial technical complaints must be reported to the sponsor by the trial-site personnel within 24 hours after being made aware of the event.

If the defect is combined with an SAE, the trial-site personnel must report the technical complaint to the sponsor according to the SAE reporting process and timelines (Section 10.5) in addition to reporting the technical complaint. A sample of the suspected product should be maintained for further investigation if requested by the sponsor.

Document Name: GCT1044-01 Protocol

Genmab Document Number: TMF-34513

Version: 4.0

#### **Contacting Sponsor Regarding Technical Complaints** 6.7.2

The names (and corresponding telephone numbers) of the individuals who should be contacted regarding technical complaint issues are listed on the sponsor contact page, which will be provided separately from the protocol.

Version: 4.0

#### 7 DOSE MODIFICATIONS AND SAFETY MANAGEMENT GUIDELINES

# 7.1 **Dose-Limiting Toxicity**

The DLT evaluation period is defined as the period from the start of the first GEN1044 administration on C1D1 of the Dose Escalation part of the trial until 7 days after the first full dose. As described in Section 4.1, if a subject receives the priming dose on C1D1, one intermediate dose on C1D8, and the full dose starting on C1D15, the DLT period will be the first 21 days of Cycle 1 (Cycle 1 days 1 through 21). If a subject receives the priming dose on C1D1, the first intermediate dose on C1D8, the second intermediate dose on C1D15, and the first full dose on C2D1, the DLT period will be Cycle 1 up to and including C2D7 (ie, a total of 28 days). The DLT evaluation period may be adjusted for potential GEN1044 treatment delay as described in Section 11.1.7.

National Cancer Institute (NCI) Common Terminology Criteria for Adverse Events (CTCAE) v5.0 (NCI-CTCAE, 2017) will be used to assess toxicities/AEs, except for CRS and immune effector cell-associated neurotoxicity syndrome (ICANS) (see Section 10.4.1 and Section 10.4.2, respectively).

A DEC is set up for the study. The DEC will review data from each DL cohort and make a decision regarding dose escalation. That decision of the DEC has to be confirmed by the sponsor SC. The DMC will review data on a quarterly basis.

Events to be collected and assessed by the DMC for DLTs include: SAEs; AESIs where applicable; and clinically significant abnormal laboratory values (that are not already covered by a separate AE term).

The occurrence of any of the toxicities outlined in this section will be considered a DLT if assessed by the investigator to be at least possibly related to GEN1044. AEs clearly not related to the trial treatment (GEN1044) such as disease progression, environmental factors, unrelated trauma, etc, should not be considered a toxicity event.

The following will qualify for a DLT:

- ≥ Grade 3 CRS, graded according to American Society for Transplantation and Cellular Therapy (ASTCT) criteria (Lee et al., 2019) (see Section 10.4.1, Table 16).
- \geq Grade 3 ICANS, graded according to the criteria specified in Table 17, Section 10.4.2.
- Any Grade 3 or 4 non-hematologic toxicity except for:
  - Grade ≥ 3 nausea/vomiting or diarrhea <72 hours with adequate anti-emetic and other supportive care
  - Grade  $\geq$  3 fatigue  $\leq$ 1 week
  - Grade ≥ 3 electrolyte abnormality that lasts <72 hours, unless the patient has clinical symptoms, in which case all grade ≥3 electrolyte abnormality regardless of duration should count as a DLT
  - Grade ≥ 3 amylase or lipase elevation NOT associated with symptoms or clinical manifestations of pancreatitis does not need to be counted as a DLT
  - o Laboratory abnormalities are excluded except for below:
    - Clinically significant medical intervention is required to treat the subject, OR
    - The abnormality leads to hospitalization, OR
    - The abnormality persists for >1 week, OR
    - The abnormality results in a drug-induced liver injury (DILI)
- Any Grade 3 or 4 hematologic toxicity, except for:

Version: 4.0

- Grade  $\geq$  3 lymphocytopenia lasting  $\leq$ 72 hours
- Grade 3 thrombocytopenia not associated with impaired hemostasis, clinically significant bleeding or required platelet transfusion therapy
- Grade  $\geq$  3 ANC lasting <7 days and without fever
- Grade 3 or grade 4 febrile neutropenia:
  - o Grade 3 is defined as absolute neutrophil count (ANC) <1000/mm³ with a single temperature of >38.3°C (101°F) or a sustained temperature of ≥38°C (100.4°F) for more than 1 hour.
  - o Grade 4 is defined as ANC <500/mm³ with a single temperature of >38.3°C (101°F) or a sustained temperature of ≥38°C (100.4°F) for more than 1 hour, with life-threatening consequences and urgent intervention indicated.
- Liver toxicity as defined by Hy's Law (FDA-Guidance, 2009) below:
  - o Aminotransferase (ALT and/or AST) >3×ULN.
  - o Total bilirubin >2×ULN, without initial findings of cholestasis (elevated serum alkaline phosphatase).
  - No other reason can be found to explain the combination of increased ALT/AST and total bilirubin.
- Any treatment-related toxicity that causes the subject to discontinue treatment during Cycle 1.
- Any grade 5 toxicity.

